5. SUBJECT ENROLLMENT

Before subjects begin participation in any study-specific activities/procedures, Amgen requires a copy of the site's written institutional review board/independent ethics committee (IRB/IEC) approval of the protocol, informed consent form (ICF), and all other subject information and/or recruitment material, if applicable (see [Section 11.2](#)).

The subject or the subject's legally acceptable representative must personally sign and date the IRB/IEC- and Amgen-approved ICF before the commencement of study-specific procedures. Upon completion of the screening period the subject is evaluated by the investigator and providing the subject continues to meet the inclusion/exclusion criteria, the subject is subsequently eligible to be enrolled in the study and either randomized or assigned to a treatment regimen.

For Phase 2, a subject will be considered enrolled into the study when the investigator decides that the subject has met all eligibility criteria and registers enrollment via IVRS.

In Phase 3, a subject will be considered enrolled and randomized into the study when the investigator decides that the subject has met all eligibility criteria and a randomization number is provided via IVRS.

Enrollment will occur after the centralized response assessment to S1 chemotherapy. Subjects with CMR (Deauville \leq 3) will not be enrolled. The investigator is to document this decision and date, in the subject's medical record and in/on the enrollment case report form (CRF).

Each subject who enters into the screening period (defined as the date when the subject signs the IRB/IEC-approved main study ICF) for the study receives a unique subject identification number before any study-related activities/procedures are performed. The subject identification number will be assigned by IVRS. This number will be used to identify the subject throughout the clinical study and must be used on all study documentation related to that subject.

Subjects who fail screening will be allowed to re-screen once.

The subject identification number must remain constant throughout the entire clinical study; it must not be changed after initial assignment, including if a subject is rescreened. This number will not necessarily be the same as the randomization number assigned for the Phase 3 part of this study.

5.1 Randomization/Treatment Assignment

Subjects enrolled during the phase 2 component will be treated with blinatumomab monotherapy. An authorized site representative will make the enrollment call to the IVRS. A phase 2 subject will be considered enrolled into the study when the investigator confirms that the subject has met all eligibility criteria and an enrollment call has been made into IVRS. The enrollment date is to be documented in the subject's medical record and on the enrollment electronic case report form (eCRF).

Subjects enrolled during the phase 3 component will be randomized to blinatumomab or IC chemotherapy in a 1:1 ratio as assigned by the IVRS in an open-label manner. The randomization will be performed by IVRS. To randomize a subject, an authorized site representative will make the randomization call to the IVRS to assign a randomization number to the subject. The randomization call to the IVRS is accomplished by entering the pertinent information detailed in the IVRS user manual. The following information will be entered into IVRS for stratification:

- Response to S1 (PMR vs NMR/PMD)
- S1 chemotherapy (ie, Cytarabine [Ara-C] administered in S1 Yes/No)
- PMBCL and B-cell lymphoma, unclassifiable, with features intermediate between DLBCL and classical Hodgkin lymphoma vs all other histologies of aggressive B-cell lymphoma

Once data have been entered into the IVRS a confirmation fax or email will be sent to the site to verify that the correct information has been entered. The site representative will receive a single, unique randomization number for each phase 3 subject and the randomization treatment assigned. A phase 3 subject will be considered enrolled and randomized into the study when the investigator confirms that the subject has met all eligibility criteria and a randomization number is assigned. The randomization date and randomization number are to be documented in the subject's medical record and on the enrollment eCRF.

Subjects should initiate their IVRS-assigned protocol required therapy within 3 days of enrollment confirmation for phase 2 and phase 3.

6. TREATMENT PROCEDURES

6.1 Classification of Product(s) and/or Medical Device(s)

The Amgen Investigational Product (IP) used in this study is blinatumomab, and non-Amgen non-IP is IC chemotherapy.

The Investigational Product Instruction Manual (IPIM), a document external to this protocol, contains detailed information regarding the storage, preparation, destruction, and administration of blinatumomab.

Other protocol-mandated medication (eg, dexamethasone used for pre-dose treatment or for treatment of adverse events) are commercially available and are not provided or reimbursed by Amgen (except if required by local regulation). The investigator will be responsible for obtaining supplies of these protocol-specified therapies.

6.2 Investigational Product: Blinatumomab

Blinatumomab will be manufactured and packaged by Amgen and distributed using Amgen clinical study drug distribution procedures.

Blinatumomab will be supplied as single-use glass injection vials as a sterile, preservative-free, white to off-white, lyophilized powder for reconstitution and administration by intravenous (IV) infusion. Each vial contains blinatumomab with additional excipients and buffers including citric acid monohydrate, trehalose dihydrate, lysine hydrochloride and polysorbate 80, pH 7.

To prepare blinatumomab for IV infusion, the lyophilized powder is reconstituted with sterile water for injection. The reconstituted solution is added to an infusion bag containing 0.9% NaCl and a product-specific stabilizer (IV Solution Stabilizer). The IV solution stabilizer functions to prevent adsorption of blinatumomab to surfaces of the infusion components. The IV Solution Stabilizer is supplied in a single-use glass injection vials as a sterile, preservative-free, clear, colorless-to-slightly-yellow liquid concentrate.

Sterile water for injection and supplies required for reconstitution and injection of blinatumomab will not be provided to clinical sites.

For information surrounding the use of a continuous infusion pump, refer to [Section 6.7](#).

6.2.1 Dosage, Administration, and Schedule

Blinatumomab will be administered by continuous IV infusion.

A cycle of blinatumomab is 70 days and includes treatment 56 days of treatment, followed by a 14-day treatment-free interval. The initial blinatumomab dose is 9 µg/day, and is escalated stepwise to 28 µg/day on day 8 and then 112 µg /day on day 15 until the completion of therapy, barring any dose modifications. Optional Cycle 2 blinatumomab consists of a 28 day cycle of blinatumomab continuous infusion administered 7 days at 9 µg/day, 7 days at 28 µg/day, and 14 days at 112 µg/day. The dosing schedule is described in the study schema in [Figure 1](#) for phase 2 and [Figure 2](#) for phase 3.

The dose, start and stop date/time, and lot number of the protocol-specified therapy are to be recorded on each subject's eCRF.

Response should be assessed 14 (+ 3) days after completion of blinatumomab infusion. Chemotherapy should not be administered within the 14-day treatment-free interval

unless clinical evidence of disease progression has occurred and therapy is indicated. Uniform adherence to that timeline is optimal for interpretation of results. Subjects receiving additional chemotherapy prior to the response assessment will be scored as nonresponders.

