All subjects enrolled in phase 2 and subjects in phase 3 randomized to the blinatumomab arm will receive a single 70-day cycle, with a total of 56 days of blinatumomab continuous infusion (7 days at 9 μ g/day, 7 days at 28 μ g/day, and 42 days at 112 μ g/day), followed by a treatment-free period of 14 days. Response will be assessed by central review of a PET/CT after this single cycle (ie, on approximately day 70).

In phase 3, subjects randomized to the IC arm will receive no more than 3 cycles (maximum cycle length 28 days) of S2 chemotherapy prior to response assessment (see specific S2 requirements in Section 6.3). Any change in the chemotherapy regimen prior to response assessment or without objective evidence of disease progression will be scored as treatment failure.

Following the response assessment, subjects may undergo hematopoietic stem and progenitor cell (HSC) mobilization and autologous hematopoietic stem cell transplant or allogeneic HSCT.

Subjects who demonstrate a response (PMR or CMR) to protocol-assigned therapy based on local assessment and who are not proceeding directly to autologous hematopoietic cell transplant or allogeneic HSCT may receive additional cycles of protocol-assigned therapy (maximum 1 x 4-week cycle of blinatumomab given 7 days at 9 μ g/day, 7 days at 28 μ g/day, and 14 days at 112 μ g/day or a maximum of 3 cycles of IC S2 chemotherapy) starting at least 2 weeks, but not

more than 4 weeks, after the end of Cycle 1. Non-responding subjects (NMR or PMD/ progressive disease [PD]) are not eligible for retreatment with blinatumomab.

Sample Size: Approximately 332 subjects will be enrolled in the study, including 36 subjects in phase 2 and 296 in phase 3. Of these, approximately 184 subjects will receive blinatumomab.

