6.8 Product Complaints

A product complaint is any written, electronic or oral communication that alleges deficiencies related to the identity, quality, durability, reliability, safety, effectiveness, or performance of a drug(s) or device(s) after it is released for distribution to market or

clinic by either Amgen or by distributors and partners for whom Amgen manufactures the material.

This includes any drug(s), device(s) or combination product(s) provisioned and/or repackaged /modified by Amgen. Drug(s) or device(s) includes IP.

Any product complaint(s) associated with an IP or non-IP(s) or device(s) supplied by Amgen are to be reported according to the instructions provided in the IPIM.

6.9 Excluded Treatments, Medical Devices, and/or Procedures During Screening and Treatment Periods

Subjects are prohibited from receiving the following therapies during the Screening and Treatment Phase of this study:

- Any anti-tumor therapy other than protocol specified therapies:
- Radiation therapy. Note that radiotherapy to previously bulky sites of disease that upon response assessment, **remains** metabolically inactive (Deauville ≤ 4) will not be counted as an event. Intrathecal chemotherapy may be administered if the investigator deems the subject to be at high risk of CNS relapse. Evidence of CNS disease will be reported as relapse or progression.
- Immunotherapy other than blinatumomab
- Chronic systemic (> 7 days) high-dose corticosteroid therapy (dexamethasone > 24 mg/day or equivalent)
- Any other immunosuppressive therapies (except for transient use of corticosteroids for ≤ 7 days)
- Any other investigational agent

Following last response assessment and prior to trial enrollment, subjects are prohibited from receiving additional chemotherapy.

The Exclusion Criteria in [Section 4.1.2](#) describe other medications that are prohibited in this study.

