10.1.2.1 AutoHSCT Analysis Set

Includes all subjects who achieve a response and undergo autoHSCT **while in remission and without any other anti-cancer treatment.**

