10.1.4 Handling of Missing and Incomplete Data

Subjects missing post baseline disease assessments will be considered not to have achieved CMR.

Subjects not experiencing events that of interest for time-to-event endpoints (eg, deaths for OS) will be censored according to rules to be detailed in the statistical analysis plan.

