4.1 Study Endpoints

4.1.1 Primary Endpoint

- CMR: CMR is determined by central radiographic assessment of PET-CT scans **ie, central review** using the Lugano Classification. Subject's CMR status is determined by whether the subject achieves CMR during the first **12 weeks** after initiation of blinatumomab.

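### Only added chemotherapy before the response scan is scored as nonresponse, and the SAP definitions of CMR and OR set no condition on other anti-cancer therapy at all

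*Protocol*

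**What the plan says.** **Scoring rules.** For blinatumomab, protocol 6.2.1 states: "Subjects receiving additional chemotherapy prior to the response assessment will be scored as nonresponders". For the investigator's choice (IC) arm of phase 3, the synopsis states: "Any change in the chemotherapy regimen prior to response assessment or without objective evidence of disease progression will be scored as treatment failure". Both rules concern chemotherapy only. The one other route to a non-CMR is missing data (protocol 10.1.4): "Subjects missing post baseline disease assessments will be considered not to have achieved CMR". SAP 9.3 has the same rule.

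**Prohibited therapy.** Protocol 6.9 bars, during screening and treatment, "Any anti-tumor therapy other than protocol specified therapies". Its list includes radiation, "Immunotherapy other than blinatumomab" and other investigational agents. It attaches no consequence for CMR. It also carries a note that begins "Note that radiotherapy to previously bulky sites of disease that upon response assessment" and says that such radiotherapy, to sites found metabolically inactive, is not counted as an event. It does not say for which endpoint.

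**SAP definitions.** SAP 4.1.1 states "Subject's CMR status is determined by whether the subject achieves CMR during the first" 12 weeks after initiation. SAP 6.2 defines CMR and OR in the same way, from the central PET-CT reading. SAP 10.5.1 analyses CMR in all treated subjects with an exact 95% confidence interval. None of these mentions other therapy.

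**Transplant endpoints.** The autologous transplant set (protocol 10.1.2.1) requires transplant "while in remission and without any other anti-cancer treatment". The SAP uses the same condition for its autologous, allogeneic and overall transplant rates.

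**The concern.** CMR is meant to measure what blinatumomab does. If another active therapy starts before the scan, a negative PET can no longer be attributed to blinatumomab. The sponsor saw this for chemotherapy and wrote a rule for it. Protocol 6.9 shows that the sponsor also regards radiation, other immunotherapy and investigational agents as anti-tumor therapy, yet none of these has a scoring rule. Copying the 6.2.1 sentence unchanged into the SAP would close the gap for chemotherapy only.

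The situation is foreseeable. A subject who stops blinatumomab early still has the PET/CT, 14 (+3) days after the last dose (protocol 6.2.2.3 and Table 6 footnotes). Protocol 7.2.4 provides for subjects who start a new anti-lymphoma treatment within 30 (±3) days of the last dose. The two windows overlap.

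At stake are the single-arm CMR estimate and the comparison with 15%, which protocol 10.2.1 ties to advancement into phase 3. The study is open label, so an unwritten rule would have to be settled case by case with the results in view.

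**Working it through.** **Inputs** (protocol 10.2.1, SAP 3.2): n = 36, null CMR rate 15%, alternative 40%, one-sided α = 0.025, stated power 90%.

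**1. The plan's own figure.** The critical value is the smallest r with P(X ≥ r) ≤ 0.025 for X ~ Bin(36, 0.15).
- r = 10: P = 0.0351, too high.
- r = 11: P = 0.0137, accepted.
- Power at 40%: P(X ≥ 11) = 0.910 for X ~ Bin(36, 0.40). The stated 90% is reproduced.

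The exact interval of SAP 10.5.1 has the same threshold. Its lower limit is 14.2% at 10/36 and 16.3% at 11/36, so one subject decides whether 15% is excluded.

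**2. A fixed number of misattributed CMRs (assumed).** Let k subjects count as CMR because of other therapy, while the remaining 36 − k respond at 15%. The false-positive chance is P(Bin(36 − k, 0.15) ≥ 11 − k).

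| k | Expression | False-positive chance | Most it can add to the CMR rate |
|---|---|---|---|
| 0 | P(Bin(36, 0.15) ≥ 11) | 0.0137 | 0 |
| 1 | P(Bin(35, 0.15) ≥ 10) | 0.0292 | 1/36 = 2.8 points |
| 2 | P(Bin(34, 0.15) ≥ 9) | 0.0587 | 2/36 = 5.6 points |

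If k CMRs are instead added on top of 36 subjects at 15%, the values for k = 1 and 2 are 0.035 and 0.080. Under either model, one such CMR exceeds 0.025.

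**3. A rate instead of a count (assumed).** Suppose a share s of subjects without a blinatumomab CMR receive other therapy before the scan, and a fraction c of these become CMR. The apparent null rate is 0.15 + 0.85·s·c.

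| s | c | Apparent null rate | P(X ≥ 11) |
|---|---|---|---|
| 2% | 20% | 15.3% | 0.016 |
| 5% | 20% | 15.9% | 0.020 |
| 5% | 40% | 16.7% | 0.029 |
| 10% | 20% | 16.7% | 0.029 |
| 10% | 40% | 18.4% | 0.054 |
| 20% | 40% | 21.8% | 0.143 |

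If such therapy is rare and seldom effective, the error rate stays below 0.025. It passes that level once s·c reaches about 2%.

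**4. With the wider rule.** Subjects given other therapy before the scan cannot be CMRs. The design keeps n = 36, r = 11, size 0.0137 and power 0.910 at true countable rates of 15% and 40%.

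**The case against.** The best reply is that protocol 6.9 already bars these therapies up to the scan. The glossary ties End of Treatment to the last assessment of the treatment phase, not the last infusion. The 70-day cycle includes the 14-day treatment-free interval, and the response PET/CT is in the Cycle 1 schedule. Chemotherapy is also what the protocol offers after discontinuation (6.2.2.3) and allows in the treatment-free interval on clinical progression (6.2.1), so a rule limited to chemotherapy fits the permitted case. Much of this stands. A reader might infer that an early discontinuer can have radiotherapy or another agent before the scan without breaching 6.9, but the documents do not establish that. What the reply leaves open is scoring: a prohibition does not say how a breach is analysed, and the important-deviation process (SAP 10.3) has no scoring rule.

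A reader might also infer that the bias is always upward. For radiotherapy this is not shown. Inclusion criterion 104 wants PET positivity demonstrated at least 6 weeks after radiotherapy, which suggests that earlier uptake is hard to interpret, so an early scan could err in either direction. The 6.9 radiotherapy note may imply that other radiotherapy is an event, but no endpoint definition says so.

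Nor do the documents support a claim of bias between the phase 3 arms, since the IC rule is also limited to chemotherapy.

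Finally, transplant follows response assessment, when other therapy is less restricted, so an explicit condition is needed more there than for CMR. That explains the difference in wording. It does not supply a rule for CMR.

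**Conclusion.** The point holds as a gap in a scoring rule. Protocol 6.2.1 covers chemotherapy only, the SAP definitions of CMR and OR cover no other therapy, and nothing else in either document turns a CMR after other anti-lymphoma therapy into a nonresponse. That such a CMR counts follows from the definitions as written; no sentence says so expressly.

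Cases should be few, mainly deviations and early discontinuers. One would matter at the margin: an assumed single misattributed CMR takes the exact false-positive chance from 1.4% to 2.9% and adds up to 2.8 points. The number of cases is an assumption, and at low assumed frequencies the error rate stays within 2.5%. The SAP plans estimation with an interval, not a formal test, so the error rates bear on the sample-size basis and the advancement criterion in protocol 10.2.1. The main weight is on phase 2, since the SAP covers phase 2 only. The change should be made, but it does not call the design into question.

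**What to change.** - In protocol 6.2.1 and in the SAP 6.2 definitions of CMR and OR, score as a nonresponder any subject who starts non-protocol anti-lymphoma therapy of any kind (chemotherapy, radiotherapy, immunotherapy, targeted or investigational agent) before the qualifying response PET/CT. This matches the condition already set for the transplant endpoints.
- Reconcile the rule with the notes in protocol 6.9. State for which endpoint the exempted radiotherapy is not an event, and whether the intrathecal chemotherapy mentioned there affects scoring. The note treats Deauville ≤ 4 as metabolically inactive, whereas protocol section 5 and Appendix D place CMR at scores up to 3; these passages must be reconciled.
- If phase 3 proceeds, use equivalent wording for the IC arm.
- List the affected subjects with the therapy, its start date and the scan date.

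**Cost.** Wording in two documents and one listing. Protocol Tables 6 to 8 already collect anti-cancer therapies. Sample size and critical value do not change. The reported CMR rate may be slightly lower. This is a scoring change only and changes no clinical management.

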6.2.1.1 Inpatient Dosing

Subjects should be monitored in a hospital for a minimum of 72 hours following initiation of therapy and for a minimum of 48 hours at each step-dose increase because of the potential adverse events associated with T-cell redistribution and potential cytokine release effects triggered by the administration of blinatumomab. Nurses/physicians trained in emergency medicine should be available for immediate intervention in case of complications. See [Section 6.2.2.1](#) regarding monitoring following dose interruptions.

6.2.1.2 Outpatient Dosing

After a subject meets the minimum criteria for inpatient administration and monitoring as described in [Section 6.2.1.1](#), and if a subject is deemed stable by the investigator, continuation of blinatumomab infusion may continue as an outpatient. See [Section 6.2.2.1](#) regarding monitoring following dose interruptions.

In the outpatient setting, either the subject will return to the study center for changes of infusion bags or the subject will be visited by a well-trained ambulant/home care service provider at specific intervals to change the infusion bag. The subject and the ambulant/home care provider will be trained and will receive written instructions for storage of the IV bags.

For the ambulant/home care provider, study-specific requirements and recording of source documentation must be completed before any study-related tasks are started. A comprehensive list of all home care services, including but not limited to the storage, handling, and administration of blinatumomab as well as mandatory procedural and data collection requirements will be separately provided in a home health care manual. Following each visit, this information will be documented on the ambulant/home care services visit worksheet and forwarded to the investigator.

In case of any adverse event in the outpatient setting, the ambulant/home care provider should directly contact the investigator at the study center for further management. Any unexpected or unusual events as well as any deviations will be communicated promptly to the investigator. The ambulant/home care professionals provide 24 hour emergency on-call service.

In addition, the subject will visit the study center for the examinations according to the Schedule of Assessments ([Table 5](#) to [Table 9](#)).

6.2.1.3 Overdose

The effects of overdose of this product are not known. The daily blinatumomab dose may be up to 10% lower or higher in order to account for possible pump inaccuracies. A dose of up to 10% higher than the intended dose may not require specific intervention. In case of overdose or medication error, the infusion should be immediately stopped. Consultation with the Amgen medical monitor is strongly recommended for prompt reporting of clinically apparent or laboratory adverse events possibly related to overdosage. Consultation with the Amgen medical monitor is also strongly recommended even if there are no adverse events, in order to discuss the minimal duration of dose interruption. If the overdose results in clinically apparent or symptomatic adverse events or additional adverse events, the subject should be followed carefully until all signs of toxicity are resolved and the adverse event/s should be recorded/reported per [Section 9](#). Resumption of blinatumomab should adhere to the guidelines in [Section 6.2.2](#).

